This study is designed as a dose-finding study of SUVO compared to placebo. Briefly, OUD patients seeking supervised withdrawal will be admitted into a clinical research unit and stabilized onto buprenorphine before being randomly assigned to study condition. All participants will then undergo a routine buprenorphine taper, followed by a post-taper phase. Participants will be randomized to receive either placebo, SUVO 20mg, or SUVO 40mg and we hypothesize that one or both doses of SUVO will improve total sleep time relative to placebo. The dose of SUVO identified as most efficacious in this study will be used in a subsequent study. This study is supported by power analyses that were conducted for both Aims 1 and 2. Primary outcomes of this study include total sleep time as measured via an ambulatory electroencephalography (EEG) device, wrist actigraphy, and self-reported sleep as well as abuse liability measures of SUVO. Participants will be referred to ongoing treatment following completion of the study and will be provided with opioid overdose education and Narcan as an additional prevention measure.

2. Objectives (include all primary and secondary objectives)

- **Primary Aim 1: Evaluate whether 20mg and 40mg suvorexant, relative to placebo, improves total sleep time among patients undergoing routine opioid withdrawal, assessed via (a) EEG, (b) actigraphy, and (c) self-report.**

- Primary Aim 2: Evaluate the abuse liability of 20mg SUVO versus 40mg SUVO relative to placebo using self-report ratings, and secondary measures that include a hypothetical purchase task and drug ratings.
 - Secondary Aim 1: Evaluate whether 20mg SUVO and 40mg SUVO decreases self-reported measures of drug effects and craving, opioid withdrawal, concomitant medication use, and self-reported stress; decreased diurnal salivary cortisol and serum cortisol/adrenocorticotropic releasing hormone; and improves treatment retention relative to placebo.
3. **Background** (briefly describe pre-clinical and clinical data, current experience with procedures, drug or device, and any other relevant information to justify the research)

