Brief Sleep Hygiene Education: During stabilization, staff will conduct a brief educational session with participants to provide information regarding appropriate sleep hygiene (Doshi et al., 2017). This session will ensure all participants have the same understanding of healthy sleep behaviors before the taper begins, to minimize the impact that differences in sleep hygiene has, and better isolate the impact of SUVO on study outcomes.

Overdose Education: During the stabilization period, participants will also complete a brief opioid overdose prevention computerized education session (developed by Co-I Dunn under NIDA R21DA035327).

Randomization to Group: Participants will be stratified into experimental group based on (a) baseline Pittsburgh Sleep Quality Index (PSQI) (<5/≥5), (b) peak SOWS ratings during buprenorphine induction (≤10/>10), (c) buprenorphine stabilization dose (<16mg/16mg), and (d) sex (M/F). Randomization will occur via a minimization procedure to balance the distribution of these characteristics

across the experimental groups. Study pharmacist staff, who have no direct participant contact, will oversee randomization and dispensing of study medications.

Taper Phase (4 days): Participants will undergo an open-label, step-wise buprenorphine taper. An open-label phase is necessary because buprenorphine placebo tablets/filmstrips are not available; however, this open-label design feature is of value because it increases the overall generalizability of the study results.

Post-taper Phase (4 days): Participants will continue study participation for four days (three nights) following buprenorphine discontinuation, to capture the full course of opioid withdrawal.

Study Medications: Double-blind study medication dosing will begin on the evening before Taper Day 1. Study medications will either be 20mg SUVO, 40MG SUVO, or placebo, which will be administered prior to bedtime. Though participants will be reminded to practice good sleep hygiene, no contingencies or consequences will be associated with their sleep behavior. This is because our extensive experience suggests that participants who are unable to sleep at night will attempt to sleep during the day; all sleep attempts will be captured by wrist actigraphy and nightly questionnaires and evaluated as outcome data. Placing contingencies on sleep parameters (such as no day-time sleeping) could also prompt attrition.

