1. ***Stanford Sleepiness Scale*** (Hoddes et al., , 1973) : A 7-point scale, which is a widely-used self-report measure of daytime sleepiness that will be collected on a daily basis.

2. *Daily Sleep Diary*: Participants will be asked to document perceived sleep continuity and quality each morning. This method is widely used as an adjunct to objective measures of sleep (Carney et al., 2012) .
3. *Pittsburg Sleep Quality Index (PSQI)*; (Carpenter & Andrykowski, 1998)): The PSQI is a widely-used self-reported measure of sleep quality and disturbance over the previous 30 days. It will be used at screening (past 30 day version) and on the final day of this study (related to study days only).

Abuse Liability Measures: Medication abuse liability will be assessed as Primary Aim 3 and will include measures such as:

1. *Study Drug Abuse Liability Ratings*: The abuse liability of the blinded study drug will be assessed each morning during the taper and post-taper phases by asking participants to rate questions pertaining to drug liking and drug effects on a 0-100 point visual analogue scale, as well as the perceived street value of the study drugs.
2. *Hypothetical Opioid Purchase Task*: This is a validated method for assessing the abuse liability of opioids as well as other drugs of abuse (Aston, Metrik, & MacKillop, 2015; Jacobs & Bickel, 1999; Kiselica, Webber, & Bornovalova, 2016) .

Opioid Withdrawal Measures: Withdrawal symptom severity will be evaluated daily, using measures such as:

1. *Visual Analog Ratings*: Self-report ratings of drug effects that include withdrawal, nausea, sick, like how I feel, sleepiness, quality of sleep, and pain will be collected on a 0 (not at all) to 100 (extremely) scale.
2. *Subjective Opiate Withdrawal Scale (SOWS)* (Handelsman et al., 1987) : A 16-item widely-used self-report measure that rates opioid withdrawal symptoms on a 4-point Likert scale.
3. *Clinical Opiate Withdrawal Scale (COWS)* (Wesson & Ling, 2003) : An 11-item scale that includes some self-report items (e.g., muscle aches, nausea) and observer-rated measures of opioid withdrawal rated on unique ordinal scales.

Secondary Study Outcomes: These measures are a comprehensive range of pharmacologically specific and general questions, and are the FDA standard for the measurement of drug effects in humans. We will use measures such as:

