Stress and Craving Measures: Several brief and validated measures (such as those below) will be used to inform potential mechanism underlying effects and whether prospective studies to examine these effects more thoroughly are warranted.

1. *Visual Analog Ratings*: Self-report ratings of opioid craving (e.g. How much do you want to use right now? How much do you want to avoid using right now? How much control would you have over using if someone offered you opioids right now?) and stress (e.g. How stressed do you feel right now? How much is opioid withdrawal contributing to your stress?)
2. *Diurnal Cortisol*: Salivary cortisol will be collected several times daily. Diurnal cortisol is a measure of HPA-axis function that affects the sleep-wake cycle (Edwards, Evans, Hucklebridge, & Clow, 2001) .
3. *Additional HPA-axis Measures*: One blood sample will be taken during the stabilization, withdrawal, and post-withdrawal periods to measure change in adrenocorticotrophic hormone to cortisol ratios. These measures have been associated with treatment outcomes in other substance using populations including cocaine use disorder (Sinha, Garcia, Paliwal, Kreek, & Rounsaville, 2006) .

b. Study duration and number of study visits required of research participants.

The entire study will consist of one screening visit and a residential stay over the course of 11 days and 10 nights. All study activities will take place at the BPRU and the Bayview CRU.

c. Blinding, including justification for blinding or not blinding the trial, if applicable.

The only blinded medication in this study is SUVO. Since this is the medication of interest, participants will be blinded to ensure study rigor and assess the utility of SUVO to treat sleep disturbance compared to placebo. The buprenorphine taper and concomitant medications will not be blinded in order to mimic the real-world experience of supervised opioid withdrawal and increase ecological validity.

d. Justification of why participants will not receive routine care or will have current therapy stopped.

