Buprenorphine: Buprenorphine is FDA-approved for the treatment of OUD and it will be used according to that indication in this study. The buprenorphine stabilization and taper will be open label. Participants will be stabilized on buprenorphine for a maximum 3 week period before study admission, and will then complete a 3-day stabilization period (e.g., 8-16mg/day) and a 4-day step-wise taper. These approaches are standard clinical practice. This study utilized the open label taper approach in order to increase ecological validity of the supervised withdrawal paradigm.

Concomitant Medications: Consistent with standard clinical practice treatment, the following concomitant medications will be available to patients upon request: ibuprofen, acetaminophen, loperamide, milk of magnesia, and simethicone. Clonidine may be provided during the induction period only. Concomitant medications introduce a necessary confound in opioid withdrawal research because they reduce the withdrawal symptom severity that is being evaluated as part of the primary study outcomes. However, our considerable experience with opioid withdrawal studies suggests that provision of some additional supportive medications is necessary to prevent treatment attrition. Following randomization to experimental group, patients will not receive additional sleep aids or clonidine. Concomitant medication use will be PRN and compared across groups as an outcome.

- b. Justification and safety information if FDA approved drugs will be administered for non-FDA approved indications or if doses or routes of administration or participant populations are changed.

Suvorexant (SUVO): Suvorexant is approved by the FDA for the indication of insomnia at a 10mg and 20mg dose, so an IND will be requested from the FDA for the doses (20mg, 40mg) proposed in this trial. The proposed 40mg dose is being evaluated because suvorexant has a broad therapeutic window, persons with OUD might have increased orexin signaling, as evidenced by postmortem studies citing 54% more orexinergic neurons in the lateral hypothalamus of persons with OUD compared to healthy controls, and because sleep disturbance during opioid withdrawal is severe and- as of yet- no sleep-promoting pharmacotherapies have been shown to be effective in human opioid withdrawal studies.

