Secondary measures will be additional ratings on the hypothetical purchase task, SOWS and VAS ratings of opioid withdrawal, VAS ratings of abuse liability, self-reported craving, self-reported stress, perceived drug value, and diurnal salivary cortisol (measured via AUC values and mean daily cortisol) and cortisol/ACTH ratios. Purchase task data will be fit to opioid demand curves for comparison. **Analyses:** All outcomes will be compared as a function of group (20mg SUVO, 40mg SUVO, and placebo) and phase (taper vs. post-taper), as well as group by day (7 nights) using area-under-the-curve (AUC). The taper and post-taper periods will then be derived and compared as a function of group and group x phase using independent groups t-tests and ANOVAs with Tukey post-hoc for pairwise comparisons. If data does not meet ANOVA assumptions, mixed model regressions will be used. Exploratory analyses will include linear and multivariate regression models to examine the relationship between measures of sleep, stress, opioid withdrawal, and craving. Logistic regression will be used to examine the relationship between sleep, stress, opioid withdrawal, and craving on the likelihood of treatment attrition.

d. Early stopping rules.

Patients will discontinue their study participation if they request to be discharged, have a serious adverse event, or if the study physicians decide it is in the patient's best interest to be removed from the study. All patients will be discharged with naloxone, opioid overdose education, and referral to outpatient OUD treatment.

8. Risks

a. Medical risks, listing all procedures, their major and minor risks and expected frequency.

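### The stabilization blood sample for the ACTH/cortisol ratio has no role in the 7.c analysis, so precision is lost and the intended change from a pre-drug reference is never estimated

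*Combined protocol and SAP*

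**What the plan says.** **Sampling.** Section 4.a, Additional HPA-axis Measures: "One blood sample will be taken during the stabilization, withdrawal, and post-withdrawal periods to measure change in adrenocorticotrophic hormone to cortisol ratios".

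**Dosing.** Section 4.a, Study Medications: "Double-blind study medication dosing will begin on the evening before Taper Day 1". Section 6.a, Buprenorphine, says that participants "will then complete a 3-day stabilization period (e.g., 8-16mg/day) and a 4-day step-wise taper". Section 4.a, Abuse Liability Measures, has the blinded drug rated "each morning during the taper and post-taper phases", which implies dosing in both phases.

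**Aim.** Secondary Aim 1 (section 2) looks, relative to placebo, for "decreased diurnal salivary cortisol and serum cortisol/adrenocorticotropic releasing hormone".

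**Analysis.** Section 7.c lists among the secondary measures "diurnal salivary cortisol (measured via AUC values and mean daily cortisol) and cortisol/ACTH ratios". The rule for that set is "All outcomes will be compared as a function of group (20mg SUVO, 40mg SUVO, and placebo) and phase (taper vs. post-taper"), with a further comparison by day over seven nights using AUC. The two phases are then "compared as a function of group and group x phase using independent groups t-tests and ANOVAs". No sentence in 7.c gives stabilization a role as phase level, covariate or reference for a change score.

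**The concern.** The stated purpose of the blood sampling is to measure change, and the sample that supplies a pre-drug starting point is left out of the analysis. Both phases that 7.c compares are on drug, so the only within-person change in the stated model runs from one on-drug sample to another. If suvorexant shifts the ratio from the first dose and holds it there, that change shows nothing.

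The group comparison does address Secondary Aim 1, but on raw levels. Differences between people that existed before dosing stay in the error term. With 12 to 15 per arm, a chance difference in baseline HPA function passes into the estimate. The minimization factors (PSQI, peak SOWS, buprenorphine dose, sex) do not include any cortisol or ACTH measure, so the allocation does not directly guard against it.

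**Working it through.** **Is there a figure in the plan to reproduce?** Not for this outcome: 7.c gives no effect size, SD, correlation or power for the ratio. The nearest figure is 95% power for an effect of 0.70 with N=36, stated for total sleep time and the opioid demand curve. Read as Cohen's f in a three-group one-way ANOVA at an assumed alpha of 0.05, the noncentrality is 36 × 0.70² = 17.64 on 2 and 33 df. Power is then 95.7%, so the stated figure reproduces as f. It is not a two-arm difference of 0.70 SD, and using 0.70 SD below is my assumption.

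**What each contrast estimates.** Let the drug shift the ratio by D in both on-drug samples and by 0 at stabilization. For drug minus placebo:

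- Group by phase (post-taper minus taper): D − D = 0.
- Group main effect (mean of the two on-drug samples): (D + D)/2 = D.
- Change from stabilization: D − 0 = D.

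A simulation of 10,000 trials (D = 0.70 SD, 15 per arm, rho 0.5) agrees. The group by phase contrast averaged −0.005 with 4.9% rejections. The group main effect averaged 0.706 with 58% rejections, and change from stabilization 0.704 with 58%.

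**What the covariate is worth.** Assumptions: unit variance at each sample, equal correlation rho among the three samples, D = 0.70 SD, two-sided 0.05, one dose against placebo, no Tukey adjustment.

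- Variance per person of the mean of two on-drug samples: v = (1 + rho)/2.
- The same after adjusting for the stabilization value: v_adj = (1 + rho)/2 − rho².
- Share of variance removed: rho² / [(1 + rho)/2].
- Standard error of the arm difference: √(2v/n). Power: noncentral t with noncentrality (D/√v) × √(n/2) on 2n − 2 df.

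| rho | v | v_adj | Variance cut | Power, n=15, without → with | Power, n=12, without → with |
|---|---|---|---|---|---|
| 0.3 | 0.65 | 0.56 | 0.09/0.65 = 14% | 63% → 70% | 53% → 59% |
| 0.5 | 0.75 | 0.50 | 0.25/0.75 = 33% | 57% → 74% | 47% → 64% |
| 0.7 | 0.85 | 0.36 | 0.49/0.85 = 58% | 52% → 87% | 43% → 78% |

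At rho 0.5 and n=15 the standard error falls from √(2 × 0.75/15) = 0.316 SD to √(2 × 0.50/15) = 0.258 SD. Charging one df for the covariate (2n − 3) lowers these powers by 0.2 percentage points at most.

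**Chance imbalance.** The baseline difference between two arms of 15 has standard error √(2/15) = 0.365 SD. At rho 0.5, an imbalance of that size moves the unadjusted contrast by 0.5 × 0.365 = 0.18 SD. At 12 per arm it is 0.5 × √(2/12) = 0.20 SD. The covariate removes this shift.

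**A simple change score is not the remedy.** Its variance is (1 + rho)/2 + 1 − 2rho. At n=15 power is 44%, 57% and 79% for rho 0.3, 0.5 and 0.7, below the covariate model at each rho, and at rho 0.3 below the unadjusted comparison too.

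**The case against.** A reader might infer that the plan compares only taper with post-taper, so that a steady drug effect cancels and cannot be found. The documents do not support that. Section 7.c also compares outcomes by group. That contrast keeps the whole of a steady effect, is unbiased under randomization, and is what Secondary Aim 1 asks for. The cancellation is confined to the group by phase term.

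The size is also open to challenge. The 0.70 comes from other outcomes and reproduces there as f, not as a two-arm difference. If both doses worked equally, f = 0.70 would mean 0.70 × 3/√2 ≈ 1.49 SD against placebo. The unadjusted comparison at n=15 and rho 0.5 would then already have over 99% power, leaving almost nothing to gain. This stands: the percentages are illustrative. The proportional variance cut depends on rho, not on the effect size.

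Two readings are inferences. The withdrawal and post-withdrawal samples are taken to be the taper and post-taper samples, and the stabilization sample is pre-drug only if drawn before the first evening dose; no draw time is given. Finally, this is a mechanistic secondary outcome that section 7.b does not name, and no outcome in 7.c has a baseline term. That limits the weight of the point but does not give the sample a use.

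**Conclusion.** The point holds as an avoidable loss of precision and an unfulfilled purpose, not as a bias or an inability to detect a steady effect. A sample collected to measure change has no assigned analysis. The group main effect remains valid; the group by phase term has only its 5% false-positive rate against a constant effect of any size.

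For correlations of 0.3 to 0.7, the covariate would cut the variance of the main contrast by 14% to 58%. At an assumed 0.70 SD that is worth 7 to 35 percentage points of power at 15 per arm and 6 to 35 at 12 per arm, and less if the true effect is much larger. The effect size, the equal correlations, the two-sided 0.05 level and the absence of a Tukey adjustment are all assumptions. This is a low-severity improvement to a secondary analysis.

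**What to change.** Give the blood ratio its own sentence in 7.c:

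- Response: the ratio at the two on-drug samples, on the log scale if skewed. Section 4.a writes ACTH to cortisol and 7.c writes cortisol/ACTH. Choose one; on the log scale the choice changes only the sign.
- Factors: group, period and group by period, with the stabilization value (same scale) as covariate.
- Main contrast: dose minus placebo, averaged over the two on-drug samples.
- State that the stabilization sample is drawn before the first study dose, and that the withdrawal and post-withdrawal samples correspond to taper and post-taper.

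A dedicated model is needed in any case: with one blood sample per period, the seven-night by-day and AUC analyses cannot be computed for this ratio.

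The cost is one degree of freedom and no new data. Participants without a stabilization sample need simple baseline imputation or drop out of this secondary model; say which in advance.

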1. *Vital Signs*: Physiological measurements of blood pressure, pulse, respiration, and oxygen saturation will be measured several times daily.
2. *Pupil Diameter*: Physiological measure of autonomic nervous system activity that is a hallmark metric of opioid withdrawal. Will be assessed several times daily using a hand-held, ambulatory pupilometer (Neuroptics; Irvine CA).
3. *Retention in Treatment*: Retention will be evaluated as number days completed (continuous) and being present on the final day of the study (yes/no).
4. *Opioid agonist/antagonist scale*: A 37-item self-report measure of opioid effects on a 5-point Likert scale.

Drug Specific Measures: Secondary aims will assess a variety of domains related to the study medication using measures such as:

1. *Drug Identification*: Upon study discharge, participants will indicate whether they believe they are receiving SUVO or placebo.
2. *Drug Satisfaction*: Upon study discharge, participants will be asked whether they would recommend the study medication (yes/no) to a family or friend experiencing sleep impairment while withdrawing from OUD.
3. *Adverse Event Ratings*: We will follow standard FDA guidelines regarding recording of adverse events and will document all events on a daily basis. AEs will be summarized descriptively by severity and relatedness.

4. *Neurocognitive Test Battery*: Participants will complete a daily battery of cognitive tests to assess whether the study medication and/or sleep impairment is associated with changes in cognitive function and psychomotor agility during the course of withdrawal. The battery will consist of the Circular Lights test of fine motor movement, the Psychomotor Vigilance Task, the Digit Symbol Substitution Task (DSST) measure of psychomotor speed/pattern recognition, and the N-back measure of working memory. These tests were selected because they can be completed quickly, are not prone to practice effects, produce robust, reliable results, and have not been aversive to previous patients during opioid withdrawal.
5. *The Hamilton Depression scale (HAM-D)*: The HAM-D is a structured clinical interview that will be used multiple times throughout the study to provide a continuous measure of depressive symptomatology (Hamilton, 1960).

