The first primary outcome for this study will be total sleep time during opioid withdrawal as determined by EEG, and supplemented by actigraphy and self-report.

The second primary outcome for this study is abuse liability, which will be assessed via next day measures of Drug Liking measured on a 0-100 point VAS.

b. Secondary outcome variables.

(1) Secondary outcomes from the Sleep Profiler EEG will include measures of sleep continuity and architecture

(2) Secondary actigraphy outcomes will include sleep and activity-related outcomes

(3) Secondary self-report sleep ratings will include self-reported sleep measures

(4) Opioid withdrawal severity, assessed via the subjective opiate withdrawal scale.

(5) Other secondary outcomes include a hypothetical purchasing task, other self-report VAS measures of abuse liability (e.g. drug effect, good effect, bad effect, perceived drug value), self-reported measures of drug craving, VAS opioid withdrawal, stress; diurnal cortisol; vital signs; and retention in treatment.

c. Statistical plan including sample size justification and interim data analysis.

Power Analyses: In order to support the planned 2 and 3 group analyses (comparing 20mg SUVO, 40mg SUVO, and placebo), we used G-power to derive sample sizes from previously reported effect sizes in clinical trials on SUVO and hypothetical opioid purchase task data; both displayed large effect sizes (≥ 0.70). A total sample size of 36 participants (12 per group) would provide 95% power to detect an effect size of 0.70 for difference in total sleep time (Primary Aim 1) and difference in the opioid demand curve (Secondary Aim 1). A study on the abuse liability of SUVO, zolpidem, and placebo in non-ODU patients (Schoedel et al., 2016) reported a medium to large effect size on drug liking (0.45), suggesting a total sample size of 34 would provide 90% power to detect an effect size of 0.45 for Primary Aim 2. To protect against participant drop out, we are proposing to enroll 15 participants per medication group (total N=45).

Analyses: All Primary Outcomes (total sleep time, opioid withdrawal severity, and abuse liability) will be compared as a function of group (20mg SUVO, 40mg SUVO, and placebo; or SUVO [collapsed] vs placebo) and phase (taper vs. post-taper), as well as group by day (7 nights) using 2-factor Proc Mixed analyses with Tukey posthoc testing. Both peak values and Area-under-the-curve (AUC) values of total sleep time, SOWS scores, and Drug Liking

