will be derived for (a) the entire study, (b) the taper period, and (c) the post-taper period. These outcomes will be compared as a function of group and group x phase using independent groups t-tests and ANOVAs with Tukey post-hoc for pairwise comparisons. If data does not meet ANOVA assumptions, mixed model regressions will be used.

Secondary outcomes from the Sleep Profiler EEG may include measures of sleep continuity (sleep latency, sleep efficiency [total sleep time/time spent in bed], wake after onset [WASO], number of awakenings) and architecture (time spent in stage 1, stage 2, stage 3, and rapid eye movement [REM] sleep). (b) Secondary actigraphy outcomes may include wake after sleep onset (WASO), time spent napping, number of naps, and total activity. (c) Secondary self-report ratings may include subjective WASO, VAS sleepiness and quality of sleep, and Stanford Sleepiness Scale score. **Analyses:** All outcomes will be compared as a function of group (20mgSUVO, 40mg SUVO, and placebo) and phase (taper vs. post-taper), as well as group by day (7 nights) using 2-factor Proc Mixed analyses with Tukey posthoc testing. Area-under-the-curve (AUC) values for the entire study and the taper and post-taper periods will then be derived and compared as a function of group and group x phase using independent groups t-tests and ANOVAs with Tukey post-hoc for pairwise comparisons. If data does not meet ANOVA assumptions, mixed model regressions will be used.

Secondary actigraphy outcomes may include wake after sleep onset (WASO), time spent napping, number of naps, and total activity. Secondary self-report ratings may include subjective WASO, visual analogue scale (VAS) sleepiness and quality of sleep, and Stanford Sleepiness Scale score. All outcomes will be compared as a function of group (20mg SUVO, 40mg SUVO, and placebo) and phase (taper vs. post-taper), as well as group by day (7 nights) using area-under-the-curve (AUC). The taper and post-taper periods will then be derived and compared as a function of group and group x phase using independent groups t-tests and ANOVAs with Tukey post-hoc for pairwise comparisons. If data does not meet ANOVA assumptions, mixed model regressions will be used.

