This study will increase our understanding of the association between sleep and opioid withdrawal symptoms, the degree to which sleep impairment contributes to opioid treatment outcomes, and the degree to which a novel FDA-approved medication (suvorexant) with low abuse liability, high safety profile, and immediate onset of action has on sleep impairment during opioid withdrawal. This will be the first study to examine this medication in opioid use disorder (OUD) patients, the first to examine any sleep pharmacotherapy with OUD patients during a withdrawal procedure, and the first to use a rigorous unobtrusive, wireless, objective EEG monitor to collect sensitive objective data regarding sleep continuity and architecture. These results will be rigorous and transparent and will advance our understanding of the role sleep may play in OUD and the value of evaluating the orexin system’s role in OUD more broadly, to ultimately provide an empirically-supported way to address the opioid epidemic.

10. Payment and Remuneration

a. Participants will earn \$30 for the screening visit. Participants who complete the study will earn \$100 per day for a total of \$1100. Participants will also earn an adherence bonus of \$30/day (up to \$300) for wearing the wireless EEG device throughout the night. The total maximum payment is \$1430 (See Payment Table).

Payment Schedule		
	Daily Payments	EEG Bonus
Screen	\$30	-
Day 1	\$100	-
Day 2	\$100	\$30
Day 3	\$100	\$30
Day 4	\$100	\$30
Day 5	\$100	\$30
Day 6	\$100	\$30
Day 7	\$100	\$30
Day 8	\$100	\$30
Day 9	\$100	\$30
Day 10	\$100	\$30
Day 11	\$100	\$30
Follow-up	\$30	-
Total	\$1160	\$300
Maximum Payment	\$1460	

11. Costs

- a. Detail costs of study procedure(s) or drug (s) or substance(s) to participants and identify who will pay for them.

The participants in this study will not pay for any aspect of study participation. All study medications, residential treatment costs, and staff support is paid through the NIHA grant **UG3DA048734-01**.

References

- Aston, E. R., Metrik, J., & MacKillop, J. (2015). Further validation of a marijuana purchase task. *Drug and Alcohol Dependence, 152*, 32-38.
- Bunce, S. C., Harris, J. D., Bixler, E. O., Taylor, M., Muelly, E., Deneke, E., . . . Meyer, R. E. (2015). Possible evidence for re-regulation of HPA axis and brain reward systems over time in treatment in prescription opioid-dependent patients. *Journal of Addiction Medicine, 9*(1), 53-60. doi:10.1097/ADM.0000000000000087 [doi]

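### The exploratory attrition regression fixes no predictor window; with the plan's AUC or peak summaries, length of stay alone can create an association with leaving

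*Combined protocol and SAP*

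**What the plan says.** The last sentence of section 7.c, among the exploratory analyses, reads "Logistic regression will be used to examine the relationship between sleep, stress, opioid withdrawal, and craving on the likelihood of treatment attrition". It does not say on which day or over which window the predictors are measured, whether they are lagged, or whether they enter together or separately.

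Section 4.a (Secondary Study Outcomes) defines the outcome: "Retention will be evaluated as number days completed (continuous) and being present on the final day of the study (yes/no"). Attrition itself is not defined separately; the yes/no form, one value per person, is the one that fits a logistic model.

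The predictors are repeated measures. For withdrawal, section 4.a says "Withdrawal symptom severity will be evaluated daily, using measures such as" several listed scales. Section 7.c reduces such series to one number per person for the group comparisons. It names the summaries as "Both peak values and Area-under-the-curve (AUC) values of total sleep time, SOWS scores, and Drug Liking". The windows for them come next in the same sentence, which says that they "will be derived for (a) the entire study, (b) the taper period, and (c) the post-taper period". It also names AUC for the secondary measures, including craving and stress, and AUC and mean daily values for cortisol. No rule covers a participant who leaves inside a window, and no landmark, lagged or time-to-event analysis appears.

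On timing, the group-by-day model covers seven nights ("as well as group by day (7 nights) using 2-factor Proc Mixed analyses with Tukey posthoc testing"), and the post-taper phase is there because "Participants will continue study participation for four days (three nights) following buprenorphine discontinuation, to capture the full course of opioid withdrawal".

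**The concern.** A leaver's record ends at exit. A whole-stay summary is therefore taken over a window whose length is fixed by the outcome being predicted. AUC is smaller for leavers because fewer days are added. Peak is lower because there are fewer chances of a high value. If symptoms climb towards the end of the stay, leavers also miss the worst days, which lowers all three summaries, the mean included. None of this requires symptoms to influence leaving. Day-to-day triggers are also averaged away.

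This is the plan's only analysis of what predicts leaving. It bears on the statement in section 9.a that the study will inform "the degree to which sleep impairment contributes to opioid treatment outcomes". For withdrawal, the artefact runs against the plan's own expectation: section 6.a offers supportive medication in order to limit attrition, so worse symptoms are expected to raise it.

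**Working it through.** **Number of leavers.** The plan gives no figure for this model, so the count comes from its sample size. Reading 0.70 as Cohen's f, with three groups, N = 36 and alpha 0.05 (assumed), the power is 0.957 against the stated 95%, so that figure is reproduced. Enrolling 45 to keep 36 implies dropout of 1 - 36/45 = 20%, or 45 x 0.20 = 9 leavers. Four predictors would have 9/4 = 2.25 leavers each. At 10-40% dropout there are 4.5 to 18 leavers, or 1.1 to 4.5 per predictor.

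**Illustration without noise.** Take seven daily scores.
- Flat at 10: someone who leaves after day 3 has AUC (sum) 3 x 10 = 30; a completer has 7 x 10 = 70. Peak and mean are equal.
- Rising from 5 to 15 in equal steps of 10/6 = 1.67: the leaver has 5 + 6.67 + 8.33 = 20, peak 8.33 and mean 20/3 = 6.67. The completer has 70, 15 and 10.

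Both people follow the same symptom course, yet AUC differs in either case, and peak and mean differ when there is a rise.

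**Simulation model.** Y(i,t) = 5 + rise x (t-1)/6 + b(i) + e(i,t), with between-person SD 4 and within-person SD 3, 45 people, seven days and about 20% leaving. Daily leaving: logit h(i,t) = a + beta x Y(i,t). Two analyses were compared at two-sided 0.05:
- whole-stay: logit P(left) = g0 + g1 x S(i), with S the sum, maximum or mean over the days observed;
- person-day: logit P(leave next | still present on day t) = c0 + c1 x day + c2 x Y(i,t).

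Trajectory, SDs and effect size are assumptions; the documents give none. One symptom score was used, not four jointly.

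**No true effect (beta = 0), rise from 0 to 10 points.**
- AUC significantly protective: 33-94% of trials.
- Peak significantly protective: 15-86%.
- Mean: about 7% at a rise of 4 points (1 between-person SD) and 40% at 10 points (2.5 SD).
- Day-1 score: 3-5% significant, both directions together.
- Person-day model: 2-7% significant, either direction.

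**True harm (beta = 0.15 per point, so exp(0.15 x 5) = 2.1 in the odds of leaving per 5 points), same rises.**
- AUC still significantly protective: 4-58%; peak: 0-14%.
- Harm correctly detected: person-day 54-60%, day-1 score 25-28%, whole-stay mean 6-39%.

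**Second parameterisation.** Between-person SD 1, day-to-day SD 0.7, true daily odds ratio 1.5, 20-35% leaving. Fitted odds ratios per SD:
- AUC: 0.23-0.24 with no rise, 0.17-0.19 with a 1 SD rise, 0.14-0.16 with 2 SD.
- Peak: 1.14, 0.83 and 0.58-0.60 respectively.
- Rises of 1 to 2 SD: person-day model 1.49-1.51; day-1 score 1.44-1.54.

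**Sleep.** With sleep assumed to fall by 1-2 hours and no true effect, sleep AUC gave a spurious association of less sleep with more dropout in 83-89% of trials, which is the direction one would expect. Peak sleep was near nominal (7% in total). The whole-stay mean went the other way in 13-26%.

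**The case against.** The strongest reply is that the plan never says attrition will be regressed on AUC or peak. Those summaries are named for comparing randomised groups, and peak only for total sleep time, SOWS and Drug Liking. Baseline, day-1 or person-day predictors would satisfy the same sentence, and early data exist: EEG from stabilization day 1 and peak SOWS during induction. That is right, so the defect is an unspecified window that leaves an invalid choice open. It still matters, because the summaries the plan does derive are the natural ones to reach for.

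A reader might infer four stronger things that the documents do not support:
- **A joint model of whole-stay summaries is planned.** Neither part is stated.
- **The reversal is near-certain.** With eight daily ratings, the 10-point rise and a truly harmful effect, AUC was significantly protective in 66% or 90% of trials and peak in 15% or 39%, depending on the assumed leaving mechanism. That rise is the steep end. With a daily odds ratio of 2 and a 1 SD rise, peak and mean keep the right sign.
- **Milder early days explain it.** The plan gives no withdrawal time course, and induction itself requires evidence of withdrawal. Much of the AUC artefact comes from adding up fewer days.
- **The sleep finding promised in section 9.a would be reversed.** For sleep AUC the artefact runs in the expected direction.

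It is also fair that this is one exploratory sentence, and that retention is separately an outcome compared with placebo under Secondary Aim 1.

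**Conclusion.** The point holds in conditional form. If AUC or peak over the observed stay is used to predict attrition, exposure is partly a count of days survived. For withdrawal, a spurious protective association would then appear in about 33-94% (AUC) or 15-86% (peak) of trials with no true effect. AUC fails even with no symptom trend; peak and mean depend on how far symptoms rise. For sleep, an AUC result would be uninterpretable rather than necessarily reversed.

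The sizes rest on an assumed trajectory, SDs and leaving mechanism, and on 20% dropout inferred from 36 and 45. The comparison of methods is firmer: the person-day model kept its error rate near nominal and detected a real effect about twice as often as a day-1 predictor. The consequence is confined to an exploratory analysis.

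**What to change.** Replace the sentence in section 7.c with a person-day (discrete-time) logistic model: among those still present, leaving on the next day is predicted from the previous night's sleep or the previous day's SOWS, craving or stress, adjusted for study day. Fit one symptom at a time, and add arm only if the number of leavers allows. State that whole-stay AUC, peak and mean are not used as predictors of attrition, and define attrition by reference to the retention outcome.

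An acceptable but less powerful alternative is a predictor from a fixed early window, with leavers counted only after it closes.

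The cost is SAP wording and a few lines of code, on daily data already collected. With about 9 leavers, estimates will be imprecise under either method and should be reported as exploratory, with confidence intervals.
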